17.3. Reporting of Adverse Events

17.3.1. Adverse Events and Device Deficiency Classification

All reported AEs and DDs will be reviewed by a Medtronic representative. Adverse Events will be classified according to the definitions provided.

Upon receipt of AEs at Medtronic, a Medtronic representative will review the AE/DD for completeness and accuracy and when necessary will request clarification and/or additional information from the Investigator. Medtronic will utilize the Medical Dictionary for Regulatory Activities (MedDRA), to assign a MedDRA term for each AE based on the information provided by the investigator.

Regulatory reporting of AEs and DDs that could have led to an SADE will be completed according to local regulatory requirements. Refer to Table 14 for a list of required investigator and Medtronic reporting requirements and timeframes. It is the responsibility of the investigator to abide by any additional AE reporting requirements stipulated by the IRB/EC responsible for oversight of the study.

APPENDIX 1 contains the Foreseeable Adverse Event List (FAL), which is a list of adverse events related to the system or procedure that have been observed in previous studies and may be experienced by subjects. This list may help to assess if an AE is unanticipated in nature.

For emergency contact regarding a UADE, SAE and/or SADE, contact a Attain Stability Quad Clinical Study representative immediately (refer to the study contact list provided in the site's study documents binder/investigator site file or refer to the Sponsor Contact Information section provided in the CIP).

Adverse Events and Deaths will be classified according to the standard definitions as outlined below:

Table 13: Adverse Event Classification Responsibilities

What is classified?	Who classifies?	Classification Parameters
Relatedness	Investigator	Device, RA Lead, RV Lead, LV Lead, Implant Tool(s), Programmer, Procedure, Cardiovascular, Heart Failure, MRI
	Sponsor	Device, RA Lead, RV Lead, LV Lead, Implant Tool(s), Programmer, Procedure
Seriousness	Investigator	SAE
	Sponsor	SAE, UADE/USADE, Device Deficiency with SADE potential
Diagnosis	Investigator	Based on presenting signs and symptoms and other supporting data
	Sponsor	MedDRA term assigned based on the data provided by Investigator
Death Classification	Investigator	Sudden Cardiac, Non-sudden Cardiac, Non-Cardiac, Unknown

An independent Clinical Events Committee (CEC) will review and adjudicate, at a minimum, all events classified by the investigator or Medtronic as procedure or system related to determine relatedness and complication or observation classifications. In addition, the CEC will also review and adjudicate all Adverse Events resulting in death.

17.3.2. Adverse Events and Device Deficiency Reporting Requirements

Regulatory reporting of AEs and device deficiencies will be recorded and reported according to local regulatory requirements. It is the responsibility of the Investigator to abide by the adverse event reporting requirements stipulated by local law and the site's IRB/EC.

Table 14: Reporting Requirements

Serious Adverse Events (SAEs)	
Investigator submit to:	
Medtronic	
Canada: Investigators are required to report SAEs to the sponsor immediately except for those SAEs that the protocol or other document (e.g. Investigator's Brochure (IB)) identifies as not needing immediate reporting. The immediate reports should be followed promptly by detailed, written reports.
 
Medical Devices Regulations, sections 59-61. A guidance for "immediately" is within 72 hours of the investigator becoming aware of the event; Report to sponsor, without unjustified delay ISO 14155:2011, sec 9.8.b).
 
EMEA: Immediately after the investigator first learns of the event or new information in relation with an already reported event.
 
All geographies: Report to the sponsor, without unjustified delay, all serious adverse events.

Regulatory authorities	All geographies: Submit to regulatory authority per local reporting requirement.
Ethics Committee	All geographies: Submit to Ethics Committee per local reporting requirement.

Sponsor submit to:	
Regulatory authorities	All geographies: Submit to regulatory authority per local reporting requirement.
Ethics Committee	All geographies: Submit to Ethics Committee per local reporting requirement.
Adverse Device Effects (ADEs),	
Investigator submit to:	
Medtronic	EMEA: Immediately after the investigator first learns of the event or new information in relation with an already reported event. All geographies: Submit in a timely manner after the investigator first learns of the effect.
Regulatory authorities	All geographies: Submit to regulatory authority per local reporting requirement.
Ethics Committee	All geographies: Submit to Ethics Committee per local reporting requirement.
Sponsor submit to:	
Regulatory authorities	All geographies: Submit to regulatory authority per local reporting requirement.
Ethics Committee	All geographies: Submit to Ethics Committee per local reporting requirement.
Serious Adverse Device Effects (SADEs), Unanticipated Adverse Device Effects (UADEs), Unanticipated Serious Adverse Device Effects (USADEs),	
Investigator submit to:	
Medtronic	US: Submit as soon as possible, but no later than within 10 working days after the investigator first learns of the event. (21 CFR 812.150(a)(1)) Canada: SADEs on the patient, the user or any other person must be reported to the Sponsor within 72 hours after it comes to the attention of the qualified investigator. It is recommended for the investigator to report safety events as soon as possible but no longer than 15 calendar days." All geographies: Immediately after the investigator learns of the event or of new information in relation to an already reported event.
Regulatory authorities	All geographies: Submit to regulatory authority per local reporting requirement
Ethics Committee	All geographies: Submit to Ethics Committees per local reporting requirement.
Sponsor submit to:	
Regulatory authorities	All geographies: Submit to regulatory authority per local reporting requirement.
Ethics Committee	All geographies: Submit to Ethics Committee per local reporting requirement.
Investigators	All geographies: Submit per local reporting requirement.

All other reportable Adverse Events	
Investigator submit to:	
Medtronic	All geographies: Submit in a timely manner after the investigator first learns of the event.
Regulatory authorities	All geographies: Submit to regulatory authority per local reporting requirement.
Ethics Committee	All geographies: Submit to Ethics Committee per local reporting requirement.
Device Deficiencies with SADE potential	
Investigator submit to:	
Medtronic	
Canada: DDs that have resulted in any of the consequences characteristic of an SAE on the patient, the user or any other person or could do so were it to reoccur must be reported to the Sponsor within 72 hours after it comes to the attention of the qualified investigator
 
EMEA: Immediately after the investigator first learns of the deficiency or of new information in relation with an already reported deficiency.
 
All other geographies: Submit or report as required per local reporting requirements.

Regulatory authorities	All geographies: Submit to regulatory authority per local reporting requirement.
Ethics Committee	All geographies: Submit to Ethics Committee per local reporting requirement.
Sponsor submit to:	
Regulatory authorities	All geographies: Submit to regulatory authority per local reporting requirement.
Ethics Committee	All geographies: Submit to Ethics Committee per local reporting requirement.
All other Device Deficiencies	
Investigator submit to:	
Medtronic	All geographies: Submit in a timely manner after the investigator first learns of the deficiency.
Regulatory authorities	
Canada: any DD that:
 
 a. has resulted in any of the consequences characteristic of an SAE on the patient, the user or any other person; These must be reported by Medtronic to the Regulator within 10 days from the date Medtronic becomes aware. or b. could do so were it to reoccur. These must be reported by Medtronic to the Regulator within 30 days from the date Medtronic becomes aware. 
All geographies: Submit to regulatory authority per local reporting requirement.

Ethics Committee	All geographies: Submit to Ethics Committee per local reporting requirement.

17.4. Subject Death

17.4.1. Death Data Collection

All subject deaths must be reported by the investigator to Medtronic on an AE form (AE with outcome of death) as soon as possible after the investigator first learns of the death. In case of death, there should be one SAE with the outcome of death reported.

In the event of a subject's death, it is recommended that the implanted system be explanted and returned to Medtronic for analysis whenever possible per local process. Local laws and procedures must be followed where applicable.

System Interrogation Data Recommendations:

- After the subject has died but prior to explant, it is strongly recommended that the system be interrogated and a full summary interrogation (Interrogate All) performed when possible, and saved in a digital format (Save-to-Media). Store one copy of the save-to-media at the site and send a copy to Medtronic.
- Make the device interrogation/save-to-media file before any programming to prevent overwriting information in the device's memory and/or distinguishing between events detected during versus before the explant procedure.
- Recommend obtaining the exact date and time of death as lower temperatures after death can cause ERI and other "event flags" to be stored in the device memory.

If the system is not interrogated, an explanation must be entered on the AE form. For ICD systems, the ventricular tachycardia (VT) and ventricular fibrillation (VF) detection capabilities must be disabled to avoid inadvertent shocks. If any system component is returned to Medtronic, internal return product reporting systems may be used to gather additional information about the returned device/component.

A copy of the death certificate, if available and allowed by state/local law, should be sent to the Medtronic Attain Stability Quad Clinical Study team. When a death occurs in a hospital, a copy of the death summary report and all relevant hospital records should be sent to the Medtronic Attain Stability Quad Clinical Study team, if available. If an autopsy is conducted, the autopsy report should also be sent to the Medtronic Attain Stability Quad Clinical Study team if available and allowed by state/local law. When the death occurs at a remote site, it is the investigative site's responsibility to attempt retrieval of information about the death. Additionally, device disposition information should be updated. In summary, the following data will be collected:

- Date of death
- Detailed description of death
- Cause of death
- Relatedness to system and/or procedure
- Device interrogation and Save-to-Media (if available)
- Device disposition information
- Death summary/hospital records (if available and allowed by state/local law)
- Autopsy report (if available and allowed by state/local law)
- Death certificate (if available and allowed by state/local law)

17.4.2. Death Classification and Reporting

Sufficient information will be required in order to properly classify the subject's death. The Investigator shall classify each subject death per the following definitions:

Cardiac Death: A death directly related to the electrical or mechanical dysfunction of the heart.

Sudden Cardiac Death (SCD): Natural death due to cardiac causes, indicated by abrupt loss of consciousness within one hour of the onset of acute symptoms; preexisting heart disease may have been known to be present, but the time and mode of death are unexpected. If time of onset cannot be determined, SCD will alternatively be defined as any unexpected cardiac death occurring out of the hospital or in the emergency room as dead on arrival.

Non-sudden Cardiac Death: All cardiac deaths that are not classified as sudden deaths, including all cardiac deaths of hospitalized subjects on inotropic support.

Non-cardiac Death: A death not classified as a cardiac death.

Unknown Classification: Unknown death classification is intended for use only when there is insufficient or inadequate information to classify the death.

Table 15: Subject Death Classification Responsibilities

What is classified?	Who classifies?	Classification Parameters
Death Classification	Investigator	Sudden Cardiac, Non-sudden Cardiac, Non-cardiac, Unknown

The Clinical Events Committee will review all deaths and provide a final adjudication of the death classification.

Regulatory reporting of Subject Deaths will be completed according to local regulatory requirements.

17.5. Product Complaint Reporting

Product complaint reporting and vigilance reporting are applicable and AEs related to any market-released device during the study must be reported. The reporting of product complaints is not part of the Attain Stability Quad Clinical Study and should be done in addition to the AE reporting requirements. Refer to local regulations for reporting requirements.

Product Complaint: Any written, electronic or oral communication that alleges deficiencies related to the identity, quality, durability, reliability, safety, effectiveness or performance of a medical device that has been placed on the market.

- Abuse: Abnormal use (definition acc. #4.1 of Meddev 2.12-1 rev8)
- Misuse: Use error (definition acc. #4.20 of Meddev 2.12-1 rev8)

It is the responsibility of the investigator to report all product complaint(s) associated with a medical device distributed by Medtronic, regardless whether they are related to intended use, misuse or abuse of the product. Reporting must be done immediately and via the regular channels for market-released products. The reporting of product complaints by the clinical team must be done according to the local Standard Operating Procedures. Medtronic will notify the regulatory authorities (e.g. Competent Authority) as applicable for the following incidents immediately upon learning of them:

- Any malfunction or deterioration in the characteristics and/or performance of a device, as well as any inadequacy in the labeling or instructions for use which led or might have led to the death or serious deterioration in the state of health of a patient, user, or other person.
- Any technical or medical reason resulting in withdrawal of a device from the market by the manufacturer.
- Any serious deterioration in the state of health, including:
 - Life-threatening illness or injury
 - Permanent impairment of a body function or permanent damage to a body structure
 - A condition necessitating medical or surgical intervention to prevent permanent impairment of a body function or permanent damage to a body structure

18. Data Review Committees

18.1. Clinical Events Committee

The study will utilize a Clinical Events Committee (CEC). At regular intervals, an independent CEC will review events and adjudicate at a minimum all system, and procedure-related events. Additionally, the CEC will provide an adjudication of the death classification for all reported deaths.

The CEC will consist of a minimum of three (3) non-Medtronic-employed physicians that are not participating investigators for the study, including a CEC chairperson.

Medtronic personnel may facilitate and participate in CEC meetings but will be non-voting members.

For AEs and deaths reviewed by the CEC, Medtronic will provide the CEC with the Investigator's description and classification and supportive documentation (when available). The CEC is responsible for reviewing the Investigator's assessment and supportive documentation (when available), reviewing applicable definitions, and determining final classifications for all adjudication parameters. For AEs, classification includes system/procedure relatedness and complication or observation. Additionally, the CEC will provide an adjudication for all reported deaths, including system/procedure relatedness and cardiac relatedness.

If the CEC disagrees with the investigator's classification of the event, the difference will be provided to the investigator. If the investigator agrees with the CEC's adjudication, the CRF documenting the AE will be updated accordingly.

If the investigator does not agree with the CEC's adjudication classification, both determinations will be provided within the final report; however the CEC's adjudication will be used for data analysis. The disagreement will also be included in reporting to ethics committees and regulatory authorities, if required.

18.2. Data Monitoring Committee

A Data Monitoring Committee (DMC) will not be utilized for this study considering:

- An independent CEC will be formed to adjudicate at minimum all system and procedure related events and all deaths.
- This study does not meet FDA's recommended criteria (Guidance for Clinical Trial Sponsors: Establishment and Operation of Clinical Trial Data Monitoring Committees) for when a study should use a DMC, primarily because the study is not evaluating the effectiveness of a treatment intended to prolong life or reduce the risk of a major adverse health outcome.
- As a result of risk analysis and mitigation efforts as outlined in Section 16, any residual risk associated with this study is considered low and acceptable.
- The Attain Stability Quad MRI SureScan LV Lead (Model 4798) is a modification of the currently market approved Attain Performa lead Models 4298, 4398, and 4598 is a modification of the currently market approved Model 4396 LV lead. The Attain Stability Quad lead Model 4798 has a similar electrode spacing as the Attain Performa lead Models 4298, 4398, and 4598.
- Study will be conducted under FDA oversight via an investigational device exemption (IDE).

19. Statistical Design and Methods

This section presents statistical considerations for the study design and provides a high-level description of planned analysis and reporting. More details will be given in a separate Statistical Analysis Plan (SAP) that will be completed before data freeze for the primary objective analysis. Any deviation to the pre-specified statistical analyses will be noted in the study report. The analysis of the study objectives will be completed when the sample size requirements (see Table 18) for all the study primary and secondary objectives are met. An interim analysis will be conducted when 360 subjects are enrolled in the study. This interim analysis is specifically designed for one of the secondary objectives (details in Section 19.2.2).

19.1. Primary Objectives

19.1.1. Primary Safety Objective

Objective

The Attain Stability Quad MRI SureScan LV Lead (Model 4798) will be considered safe if the probability of subjects free of Model 4798 lead-related complications at 6 months post-implant is greater than 87% (i.e., the lower bound of a one-sided 97.5% confidence interval must be greater than 87%).

Hypothesis:

$$H_0: S_{(6\text{-month})} \leq 87\%$$

$$H_1: S_{(6\text{-month})} > 87\%$$

where $S_{6\text{-month}}$ is the probability that a subject remains free from Model 4798 lead related complications through 6 months since implant.

Endpoint Justification

The study primary safety endpoint is Attain Stability Quad MRI SureScan LV Lead (Model 4798) related complications. All reported system and procedure-related AEs will be reviewed by an event review committee for LV lead relatedness and severity (see Section 18.1).

Utilizing lead related complication free survival probability to evaluate lead safety performance is widely accepted across cardiac device manufacturers and in the medical literature. Current already market-released Quadripolar LV lead 6-month safety performance is summarized in Table 16. The population performance of the Attain Stability Quad MRI SureScan LV Lead (Model 4798) is expected to be similar to the Medtronic Attain Performa Model 4298 lead.

Table 16: Safety Performance of Market Released Quadripolar Lead

	Medtronic Attain Performa²⁰	St. Jude Medical Quartet²²	Boston Scientific ACUIITY X4²³
6-month LV Lead Complication Free Survival Probability Estimate	Model 4298 (Canted): 96.0% Model 4398 (Straight): 98.8% Model 4598 (S-shape): 96.2%	96% at 3 months	Straight: 96.5% Spiral: 98.5%

[figure not shown]
Statistical Analysis Methods

The primary objective will be analyzed using the time-to-first event Kaplan-Meier survival analysis method. Time 0 will be the day a subject undergoes the implant procedure of a Attain Stability Quad MRI SureScan LV Lead (Model 4798), which will be independent of success status of this implant procedure. Event date is the onset date of a subject's first complication that is related to the Attain Stability Quad MRI SureScan LV Lead (Model 4798) according to CEC adjudication. Subjects who undergo an Attain Stability Quad MRI SureScan LV Lead (Model 4798) implant attempt and do not experience any LV lead related complications will be censored at the time of their last known exposure to the Attain Stability Quad MRI SureScan LV Lead (Model 4798) for the survival analysis. For any lost-to-follow up subject, the last contact date will be used as the censor date. The 1-sided 97.5% confidence limit lower bound for the survival probability at 6 months (183 days) will be calculated using the log-log survival function approach (Kalbfleisch and Prentice 2002).

Sample Size Consideration

The primary safety objective performance criterion is set to be identical to Medtronic's Attain Performa Clinical Study (IDE Number: G120213). Therefore, the sample size calculation assumptions are derived based on the Model 4298 lead study results. The Attain Performa Model 4298 lead reported a 6-month complication free survival probably of 96.0%, with 97.5% Confidence Lower Limit of 94.3% (PMA-s clinical report).

The binomial calculation (Z-test) is used for initial sample size estimation. In order to preserve the overall study power, a type II error less than 10% was used for the sample size calculation. A sample size of 170 subjects completing their 6-month visit achieves greater than 90% power to detect a difference of 7% using the one-sided binomial test. The target significance level is 0.025. These results assume that the population proportion under the null hypothesis is 87% with an expected value of 94% (Figure 5). To account for 15% attrition, the enrollment size for this objective is 200.

Figure 5: Primary Safety Objective Sample Size Consideration by Difference Performance Assumption**Determination of Patients / Data for Analysis**

All consented subjects who undergo an Attain Stability Quad MRI SureScan LV Lead (Model 4798) implant attempt will be included in the analysis cohort. If a patient experiences multiple Attain Stability Quad MRI SureScan LV Lead (Model 4798) implant procedures during the study, the analysis cohort will only consider the first procedure. In the event multiple complications occur, the survival analysis endpoint is reached when the first Attain Stability Quad MRI SureScan LV Lead (Model 4798) related complication occurs.

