11.2. Endpoints

11.2.1 Primary Endpoints

Primary Safety Endpoint

The study primary safety endpoint is Attain Stability Quad MRI SureScan LV Lead (Model 4798) related complications through 6 months post implant. All reported system and procedure-related AEs will be reviewed by an event review committee for LV lead relatedness and severity (complication vs observation, refer to 17.1.2 for definitions).

Primary Efficacy Endpoint #1

The Model 4798 LV lead has sixteen (16) programmable pacing vectors. The endpoint for the primary efficacy objective is whether or not there is at least one Model 4798 LV lead pacing vector with pacing

capture voltage thresholds less than or equal to 2.5V (with absence of PNS at 5.0 V). This endpoint will be measured at the 6-month post implant follow-up visit.

Primary Efficacy Endpoint #2

The co-primary efficacy endpoint is whether or not a second Model 4798 lead configuration has a pacing capture threshold less than or equal to 4V (with absence of PNS at 5.0 V), excluding the pacing vector that is already counted to the primary efficacy endpoint #1. This endpoint will be measured at 6-month post implant follow-up visit.

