Final device interrogation/save- to-media		✓	✓ (CareLink transmission is acceptable for remote visits)	✓	✓	✓ (CareLink transmission is acceptable for remote visits)	✓ (required only if subject exits prior to 6 months post- implant visit; CareLink transmission is acceptable)
AE Assessment		✓	✓	✓	✓	✓	✓
Exit Subject							✓
Adverse Events (incl. AE with outcome of death)	As they occur						
Device Deficiencies							
System Modifications							
Study Deviations							

Table 9 below specifies permitted time windows for the required subject visits. Subject visit target dates and windows for each follow-up will be made available to the study site. Should a subject miss a visit or the visit falls outside the pre-specified window, a study deviation must be reported and the original follow-up schedule maintained for subsequent visits. Data analyses will include follow-up visits, regardless of whether the visit occurs within the window. Therefore, a late visit is preferred over a missed visit but must be accompanied by a deviation.

Table 9: Visit Windows

Visit	Window
Implant	0-30 days since Baseline Assessment
	(days since implant)
Pre-hospital discharge	0-7
3-month	76 - 106
6-month	183 - 213
12-month	350 - 380
18-month	518 - 578
24-month	701 - 761

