15.8.2.5. Pre-Hospital Discharge CRT System Testing and Programming

The following electrical testing will be performed using the implanted CRT-P or CRT-D device and the device programmer once the leads are connected to the CRT-P or CRT-D and pre-hospital discharge:

Lead Impedance

- Collect LV Lead Impedances using Vector Express on all vectors
- Perform a manual LV Lead Impedance Test for missing Vector Express values on vectors LV1 to RVcoil/Can, LV2 to RVcoil/Can, LV3 to RVcoil/Can, LV4 to RVcoil/Can and the final programmed vector
- Retain printouts at the site

Pacing Capture Thresholds (PCT)

- Perform PCTs at 0.5ms pulse width using Vector Express on all 16 vectors
- NOTE: A onetime manual reprogramming the pulse width to 0.5ms will be required (Out of the box pulse width is set at 0.4ms)
- Perform a manual PCT test at 0.5ms pulse width for missing Vector Express values on vectors LV1 to RVcoil/Can, LV2 to RVcoil/Can, LV3 to RVcoil/Can, LV4 to RVcoil/Can and the final programmed vector
- Retain printouts at the site

Phrenic Nerve Stimulation (PNS)

- Test for presence of PNS at 8.0V at 0.5ms on final programmed vector
- NOTE: If PNS is present at 8.0V at 0.5ms, measure the PNS threshold at 0.5ms
- NOTE: PNS observed during this testing will not be considered an AE

Other Data Collection

Other data collected prior to hospital discharge following the implant includes;

- Rationale for selecting specific LV lead pacing vector for final programming
- Final device interrogation/save-to-media
- AE Assessment
- Study deviations
- Device deficiencies

15.9. 3 Months Post-Implant (remote or in office visit)

The 3 month scheduled follow-ups may be done remotely or in office. For remote visits, CareLink transmissions may substitute device interrogations. The following procedures will be completed and data will be collected at the 3 month Follow-up visit;

Lead Impedance

- Obtain LV Lead Impedance Test for the final programmed vector
- Retain printouts at the site

Pacing Capture Thresholds (PCT)

- Obtain PCTs at 0.5ms pulse width on the final programmed vector
- NOTE: A onetime manual reprogramming the pulse width to 0.5ms will be required (Out of the box pulse width is set at 0.4ms)
- Retain printouts at the site

Phrenic Nerve Stimulation (PNS) (in office visit only)

- Test for presence of PNS at 8.0V at 0.5ms on final programmed vector
- NOTE: If PNS is present at 8.0V at 0.5ms, measure the PNS threshold at 0.5ms

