19.1.2. Primary Efficacy Objective #1**Objective**

The Attain Stability Quad MRI SureScan LV Lead (Model 4798) will meet the first primary efficacy objective if the proportion of subjects with at least one Attain Stability Quad MRI SureScan LV Lead (Model 4798) pacing vector having a pacing capture threshold (PCT) less than or equal to 2.5 V at 0.5ms pulse width (with absence of PNS at 5.0 V) at 6 months post-implant is greater than 80% (i.e., the lower bound of the one-sided 97.5% confidence interval must be greater than 80%).

Hypothesis

$H_0: P_{1_{6\text{-month}}} \leq 80\%$

$H_A: P_{1_{6\text{-month}}} > 80\%$,

[figure not shown]
where $P_{1_{6\text{-month}}}$ is the proportion of subjects with pacing voltage thresholds $\leq 2.5\text{V}$ at 0.5ms (with absence of PNS at 5.0 V) at 6 months follow-up visit post-implant for at least one LV lead pacing vector.

Endpoint Justification

The Attain Stability Quad MRI SureScan LV Lead (Model 4798) is equipped with the identical four electrodes to the Attain Performa LV leads. At the same time, the unique fixation mechanism may cause the distal end of the lead (tip) to be implanted away from the apical region of the heart, and therefore

the PCT may be slightly higher than the values observed in other Quadripolar LV leads. Therefore, we simulated the lead pacing threshold values based on the Attain Performa IDE study data, but excluding the PCT values collected at the most distal electrode. The simulation estimated that 89% of the subjects will achieve this endpoint (Figure 6).

Figure 6: Simulated PCT Distribution

Statistical Analysis Methods

All subjects with valid pacing thresholds measured at the 6 month follow-up visit will be included in this analysis. The proportion of subjects having at least one LV lead pacing vector with voltage thresholds less than or equal to 2.5V (with absence of PNS at 5.0 V) will be calculated. The lower bound of the 1-sided 97.5% Confidence Interval will be calculated using the Exact binomial method. Any subject in which no valid pacing threshold value is measured or who has an unable-to-capture result via all LV lead pacing vectors will be reviewed and adjudicated for a possible lead related AE but will not be included for this evaluation if the occurrence is deemed to be a system related event (e.g. lead dislodgement). However, this event may be counted against the safety primary endpoint based on the CEC's final classification.

Sample Size

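### A system-related loss of capture found at the 6-month visit and dated after day 183 may be counted in neither the primary efficacy nor the primary safety endpoint

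*Protocol*

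**What the plan says.** **Safety (Protocol 11.2.1 and 19.1.1).** The endpoint is lead "related complications through 6 months post implant". The analysis is Kaplan-Meier time to first complication as adjudicated by the CEC. "Event date is the onset date of a" subject's first such complication, and the "lower bound for the survival probability at 6 months (183 days) will be calculated".

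**Visit timing (15.4, Table 9).** The 6-month window is days 183 to 213 after implant. Late visits are also used: "Data analyses will include follow-up visits, regardless of whether the visit occurs within the window".

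**Earlier lead testing (15.9).** The 3-month visit (days 76 to 106) may be remote. Its threshold requirement is limited: "Obtain PCTs at 0.5ms pulse width on the final programmed vector". After discharge, the 6-month visit is the first scheduled test of all 16 vectors (15.10, Table 8).

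**Efficacy #1 (19.1.2).** A subject with no valid threshold, or no capture on any vector, "will not be included for this evaluation if the occurrence is deemed to be a system related event (e.g. lead dislodgement"). The stated counterpart is that "this event may be counted against the safety primary endpoint based on the CEC" classification.

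**Efficacy #2 (19.1.3).** The cohort again needs at least one valid threshold. Failure to capture is scored as a failure only where no lead related event was reported.

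**Sensitivity analysis (19.3.2).** Successfully implanted subjects who fall outside the efficacy cohort are set to failure in a worst-case analysis.

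**The concern.** The efficacy rules hand a class of failures to the safety endpoint. That is defensible only if safety can receive them. Safety is read on the first day of the visit window, by onset date, so a failure found at the visit and given a later onset arrives after the reading. The subject is then in neither efficacy denominator and is not an event in the safety estimate.

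Nothing in the protocol extends the horizon to the visit, or says how to date the onset of a silent failure first seen there. The primary result in such a case depends on a dating decision taken after the failure is known. Wherever the gap operates it favours the device, in co-primary results intended for a regulatory submission.

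**Working it through.** **1. The plan's own figures.** None of them depends on this point.
- Attrition: 170/0.85 = 200 and 400/0.85 = 471 (rounded up), as stated.
- Efficacy #1: exact binomial, n = 145, 80% vs 90%; at least 126 successes needed; power 91.3% (stated 91%).
- Safety: n = 170, 87% vs 94%. The stated power above 90% reproduces with a Z-test using the observed-proportion variance (at least 156 of 170; 91.2%, attained one-sided alpha 0.036). With the null variance or the exact test it is 85.6%.

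**2. Timing.** The window has 213 − 183 + 1 = 31 days. Of these, 213 − 183 = 30 (97%) lie after the safety horizon.

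**3. Where a failure found at the 6-month visit is counted.**

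| Finding at the visit | Safety at day 183 | Primary efficacy |
|---|---|---|
| No capture on any vector or no valid threshold; system/lead related; onset dated ≤ 183 | Event, if adjudicated a lead complication | Left out |
| Same, onset dated > 183 | Not an event | Left out |
| At least one valid threshold remains | By onset date | Kept; can fail |

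Only the second row is lost. Its efficacy exclusion stands even when the late onset date is correct. Its safety omission is an error only when the true onset was on or before day 183 and was dated too late.

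**4. Size.** The number h in the second row is not in the documents. I assume 4 to 8 of 400 (1% to 2%) and show a wider range.

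Safety, with no censoring before day 183 and d events among n: S = 1 − d/n, and the lower bound is S^exp(1.96·se), with se = √[d/(n(n−d))] / |ln S|.

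For n = 400, d = 24 (the expected 94%): se = √[24/(400·376)]/0.0619 = 0.204; bound = 0.94^exp(0.400) = 0.94^1.492 = 0.912.

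Efficacy #1 takes the simulated 89% from 19.1.2, 356/400, with an exact lower bound; the h dropped subjects are added back as failures, 356/(400+h).

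| h | Safety estimate if counted | Safety bound (needs > 0.87) | Efficacy #1 estimate | Efficacy #1 bound (needs > 0.80) |
|---|---|---|---|---|
| 0 | 94.0% | 0.912 | 89.0% | 0.855 |
| 4 | 93.0% | 0.900 | 88.1% | 0.846 |
| 8 | 92.0% | 0.889 | 87.3% | 0.836 |
| 16 | 90.0% | 0.866 | 85.6% | 0.818 |

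**5. Reversal point.** At n = 400, 38 events pass (bound 0.8718) and 39 do not (0.8690), so 39 − 24 = 15 omitted failures would reverse the safety result. At the stated minimum of 170 with 10 events (bound 0.893), at most 13 pass, so 4 would reverse it.

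**The case against.** The case against is substantial and narrows the point.

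- **Onset is not detection.** The AE form carries the date of the event, and the CRF separately holds the date the site became aware (21.2). A dislodgement found on day 195 but dated on or before day 183 counts in safety. This stands: a reader might infer that failures found at the visit can never, or usually cannot, reach the safety endpoint, and the documents do not support that.
- **A true onset after day 183 is correctly outside a 6-month endpoint.** This stands for safety. It does not justify leaving the subject out of efficacy as well.
- **The group is small.** The 3-month visit, remote or not, tests the programmed vector, and adverse events are reported as they occur. Total failures that persist unseen to the 6-month visit are therefore mainly those arising after about month 3. Subjects with any valid threshold stay in both efficacy cohorts. This stands.
- **Section 19.3.2 already scores these subjects as failures.** It does so for efficacy only, and only as a sensitivity analysis. Its opening sentence places all implanted subjects in the primary efficacy datasets, which conflicts with the cohort conditions in 19.1.2 and 19.1.3 and should be reconciled.
- **A window opening at day 183 is sound.** Every in-window attendee is observed through the horizon. This stands; the window is not the defect.
- **Onset dating can be left to the SAP.** That answers a missing convention. It does not answer three rules the protocol itself fixes (horizon, event date, efficacy exclusion) that do not fit together.

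**Conclusion.** The gap is real but narrow. A system-related total failure to capture, or absence of any valid threshold, found at the 6-month visit and dated after day 183 may enter neither primary endpoint. Efficacy is then overstated. Safety is overstated only if a silent failure's onset is dated at discovery.

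On the assumed 4 to 8 cases at n = 400 with 24 counted events, the safety bound drops by 0.012 to 0.023 and the efficacy #1 bound by about 0.010 to 0.019. Neither conclusion changes; 15 omitted failures would be needed to reverse safety. The four-case reversal applies only at n = 170, and the study plans for 400 subjects at 6 months.

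A reader might take a rate from Table 24 (device capturing issue 0.89%, lead dislodgement 0.92%, device dislocation 3.30% of subjects). That table pools eight studies without regard to follow-up time. It is not confined to LV leads, to loss on all vectors, or to failures first found at a 6-month visit, so it gives no usable estimate of h.

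The correction matters for the accuracy of the reported estimates and for removing an unguided decision from the primary analysis. It is worth making, but does not threaten the design.

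**What to change.** Adopt one of two changes, in the protocol and carried into the SAP.

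1. In 19.1.1, state that a CEC-adjudicated Model 4798 complication first detected at or before the 6-month visit counts as an event by 6 months, assigned to day 183 if later. Keep the day-183 onset-date estimate as a sensitivity analysis.
2. In 19.1.2 and 19.1.3, state that a subject is excluded from efficacy only if the event was counted in the day-183 safety endpoint, and is otherwise an efficacy failure.

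Do not move the Kaplan-Meier reading to day 213. That would depart from the 6-month criterion, which 19.1.1 sets identical to the earlier Attain Performa study, and from the 6-month benchmarks in Table 16.

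**Cost.** One sentence, and no change in sample size. Option 1 gives a slightly lower safety estimate that may include a few events with true onset after day 183. With at least 362 of 400 event-free required (400 − 38), exact binomial power is 99.8% at a true rate of 94%, 97.6% at 93% and 88.3% at 92%. Option 2 leaves the safety estimate unchanged and lowers the efficacy estimate by the amounts in the table above.
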